### 7.3. Exclusion criteria

The participants who meet any of the exclusion criteria listed below must be excluded from participating in the trial: psychiatric diagnosis; severe cognitive impairment; hearing/visual loss.

### 8. Project tasks and assessments

The current project is composed by four tasks:

- Task 1 Development and design of the interactive platform and the app;
- Task 2 Development of the psycho-educative sessions for adolescents and parents;
- Task 3 Perform the longitudinal study with a mixed design;
- Task 4 Evaluation of the impact of the intervention and development of the final report; production of scientific papers and dissemination of the results.

### 8.1. Task 1: Development and design of the platform and the app

Task 1 will includes the development of the interactive platform and the app to support the intervention (Task 3).

New health ICT is broadly defined as the use of information and communication technology in health care to support the delivery of patient or population care or to support patient self-management. Health ICT can support patient care related activities and has been demonstrated to improve health care quality. ICT have a key role on improving the well-known "4 P": personalized, participatory, preventive and predictive medicine.

In task 1, our team will develop a platform and an app to provide (and collect) developmental adequate information on nutrition and exercise, stimulate the discussion among adolescents on the promotion of healthy lifestyles, enhance the problem-resolution skills and share strategies. It further intends to enhance cohesion among adolescents and promote the change of health behaviors. We will develop a storytelling video to support the introduction to the platform, the app and the contents presented.

ICT support will be used in two different ways:

(a) Interaction within the platform and the app

In order to attain our aims, our team will develop an e-platform and an app which will comprise:

- Presentation of strategies for promoting food security, healthy lifestyles and preventing disordered eating. We will motivate the adolescents to comment the suggested strategies and propose new ones.
- Nutritional and physical activities.
- Culinary tips with healthy and low cost meals.
- (b) Preparation of the psycho-educative sessions

Psycho-educative sessions at T1 will be prepared taking into account the contents shared in platform (see 8.2.).

## 8.2. Task 2: Development of the psycho-educative sessions for adolescents and their parents

In task 2, we will develop the separate psycho-educative sessions for adolescents and parents. Psycho-educative sessions at T0 for parents and adolescents will be based on previous clinical experiences of the team. We will develop group dynamics in order to be able to discuss the strategies for promoting healthy lifestyles and the well-being in adolescence. We will deliver leaflets with culinary tips including healthy and low cost meals.

Psycho-educative sessions at T1 for adolescents and parents will be prepared taking into account the contents shared in the platform and in the app. We will propose inhere an awards activity. Adolescents will be invited to rate the strategies presented in the e-platform and the app.

### 8.3. Task 3: Perform the study

In Task 3, we will conduct a longitudinal study with a mixed design. The intervention will last 3 months. Adolescents will be followed over 6 months.

Baseline, 3-month and 6-month evaluations will be conducted to collect anthropometric data (BMI, waist circumference and fat mass) and to apply validated questionnaires to adolescents and parents. In order to evaluate the economic determinant of food security, parents will answer to the food security questionnaire. Adolescents will answer to:

- Socio-demographic questionnaire;
- Physical and eating health questionnaire, adapted from Health Behaviour in Schoolaged Children (2010) and from Project Eat (18) (to evaluate the contextual determinants of food security);
- Nutrition questionnaire (NUT-Q, Raich et al., 2008);
- Eating Attitudes Test-26 (EAT-26; Garner & Garfinkel, 1979);
- Contour Drawing Rating Scale (CDRS; Thompson & Gray, 1995);
- EADS-21 (Lovibond & Lovibond; validated by Pais-Ribeiro, Honrado, & Leal 2004)
- Adolescent anthropometric data (weight, height, BMI, waist circumference and fat mass).

In each classroom, an identification of the group leader will take place with the purpose of facilitating adherence.

In both, platform and app, adolescents can choose to use a nick name to protect their identity. The adolescents will be presented to life situations and simulated cases and will be stimulated to present specific strategies directed to the promotion of food security and healthy lifestyles based on the cases presented. Adolescents will be motivated to comment the suggested strategies among them.

Culinary tips including healthy and low cost meals and physical activity tips will also be included. Adolescents will be stimulated to experiment these contents and comment on them.

# 8.4. Task 6: Evaluation of the impact of the intervention and development of the final report, production of scientific papers and dissemination of the results

This task is dedicated to the organization and systematization of all collected information and results, aiming at the evaluation of the impact of the intervention and at its dissemination for the scientific community. The program effectiveness evaluation will result in a final report on strategies for the prevention of food insecurity and disordered eating, and for the promotion of well-being in adolescence.

We plan to deliver four manuscripts to be submitted to peer review journals (ISI indexed).

- (a) Study 1. The data collected in T0 will be used for the first manuscript. The manuscript will be a quantitative and transversal study. We will identify: adolescents with food insecurity; and variables associated with food insecurity. We schedule its submission in November 2016.
- (b) Study 2. The data collected in T0 will be used for the second manuscript. The manuscript will be a quantitative and transversal study and will focus on the relationships between food insecurity, well-being and disordered eating. Specifically, we aim to test whether well-being is a mediator variable

- between food insecurity and disordered eating; and whether sex is a moderator variable. We schedule its submission in December 2016.
- (c) Study 3. The data collected in T0 will be further used in the third manuscript. This manuscript will be a quantitative and transversal study and will focus on the impact of adolescents' family SES in food security, well-being and disordered eating. We schedule its submission in December 2016.
- (d) Study 4. In the fourth manuscript, we will use the data collected on-line (suggestions and reflections) during the 3-month intervention. The manuscript will be a qualitative study and will focus on the strategies pointed by the adolescents to motivate other adolescents to prevent food insecurity. We schedule its submission in March 2017.
- (e) Study 5. The data collected in T0, T1 and T2 will be used in the fourth manuscript. This manuscript will be a quantitative and longitudinal study and will evaluate the intervention impact on several indicators (e.g., physical and nutritional status, eating attitudes, body image and anthropometric data) across time. Specifically, we aim to study the impact of the intervention on the adolescents who were identified as food insecure in study 1. We schedule its submission in April 2017.

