with poor well-being and psychosocial functioning (12), risk of suicidal behaviors (13) and overweight status (14, 15). Because of decreased financial resources of the families, increasing sedentary life styles and poor eating habits, adolescents are more likely to experiment adverse health conditions. Eating disorders (e.g., anorexia, binge eating, and eating disorders without other specification) and obesity are more likely to occur during adolescence (16). Portugal has one of the highest overweight prevalence rates in Europe (17). Several studies have pointed a paradoxical association between household food insecurity and overweight status in children (14, 15).

In the project *E-therapeutic intervention program for obese adolescents and their family*, funded by the Foundation for Science and Technology (PTDC / DTP-PIC / 0769/2012) and coordinated by [name], an e-platform was developed aimed to support and to manage adolescent obesity (Next.Step). The preliminary results showed that the platform is effective in promoting healthy behaviors, suggesting the relevance of technological tools as catalysts of behavioral change in Portuguese adolescents. So, based on our previous knowledge on e-intervention tools for adolescents, we intend to design a new platform and an app to promote healthy life styles, and promote food security as well as prevent disordered eating including obesity among adolescents.

Research on the association between food insecurity and well being in adolescence is scarce. Little is known about the effectiveness of interventions to reduce food security by promoting healthy life styles and psychological well-being and preventing disordered eating. Based on the literature search, we hypothesized that: (i) At 3 and 6 months adolescents will show lower indicators of food insecurity compared to the indicators of food insecurity at baseline; (ii) psychological well-being variables mediate the relationship between food insecurity and disordered eating.

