### 5.4. Primary endpoints

- Changes in indicators of nutritional habits (preference towards healthy foods, perceived benefits of healthy eating, fast food intake, family meal frequency, having breakfast on a regular basis; attitudes regarding eating) among these adolescents at 3 and 6 months.
- Changes in food insecurity in households (based on the Food Insecurity Questionnaire) at 3 and 6 months;

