### 11.2. Statistical methods

Quantitative analysis will be performed with SPSS and AMOS. In the quantitative analysis, continuous variables will be reported as mean and standard deviation. Qualitative analysis will be performed with NVivo program.

In Study 1, we will perform clusters analysis in order to identify adolescents with food insecurity. In Study 2, we will perform structural equations modeling in order to analyze whether well-being is a mediator variable between food insecurity and disordered eating, and whether sex is a moderator variable. Multilevel analysis will be performed in Study 3. In Study 4, in order to analyze the qualitative data we will conduct Thematic Analysis (NVIVO program). Finally, in Study 5, we will conduct repeated-measures factorial ANOVASs for each variable; the analyses will be complemented with multiple comparisons using Bonferroni adjustment at p < .05.

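### Study 5 focuses its impact evaluation on adolescents picked as food insecure at T0 and compares them with that same T0, so regression to the mean is expected to show a fall in food insecurity without any effect

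*Protocol*

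**What the plan says.** - **Classification.** In section 8.4, on Study 1: "The data collected in T0 will be used for the first manuscript". Section 11.2 gives the method: "In Study 1, we will perform clusters analysis in order to identify adolescents with food insecurity". The clustering variables and the boundary between groups are not stated.
- **Impact evaluation.** In section 8.4, on Study 5: "The data collected in T0, T1 and T2 will be used in the fourth manuscript". Study 5 "will evaluate the intervention impact on several indicators (e.g., physical and nutritional status, eating attitudes, body image and anthropometric data) across time", and the text then narrows the focus: "we aim to study the impact of the intervention on the adolescents who were identified as food insecure in study 1".
- **Comparison.** Hypothesis (i) in section 4 is against baseline: "At 3 and 6 months adolescents will show lower indicators of food insecurity compared to the indicators of food insecurity at baseline". Section 5.4 lists as a primary endpoint "Changes in food insecurity in households (based on the Food Insecurity Questionnaire) at 3 and 6 months".
- **Analysis.** Section 11.2 plans a repeated-measures factorial ANOVA for each variable, with Bonferroni-adjusted multiple comparisons at the 0.05 level.
- **Control.** Sections 3, 6 and 8.3 describe one group of about 300 adolescents, all receiving the intervention. Section 7.2 calls the study randomised and controlled, but no arms or allocation are described anywhere.

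**The concern.** The T0 values do two jobs. They decide who counts as food insecure, and they are the reference from which improvement is measured. A high T0 score is partly lasting level and partly measurement error or a passing bad spell. The second part does not carry over to T1 and T2, so the selected group's mean is expected to fall whatever the programme does. With no concurrent control group selected in the same way, that fall cannot be separated from an effect.

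Food insecurity is a primary endpoint and the subject of hypothesis (i), and section 8.4 says the final report is to cover strategies for preventing it. A programme with no effect could therefore be reported as reducing food insecurity in the group the project most wants to help. The Bonferroni adjustment deals with the number of comparisons. It does not remove a bias in the comparison itself.

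**Working it through.** The protocol gives no figure to reproduce: 300 is stated as an expected number, without effect size, SD or power. The size of the artefact therefore needs assumptions.

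**Inputs from the protocol.** N = 300 (section 11.1). Two illustrative shares classed as food insecure (section 4): 49.0% (Portuguese primary care attendees), 0.49 × 300 = 147; and 14.3% (US households), 0.143 × 300 ≈ 43. Neither population is this one; they only set a range.

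**Assumptions not in the protocol.** Standard normal scores, with higher meaning more insecure; selection of the top share p on the food-insecurity score alone; T0 to follow-up correlation r from 0.6 to 0.9; no true effect.

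**Expected fall.** With c = z(1 − p), the selected group has T0 mean m = φ(c)/p and the expected fall is (1 − r) × m.

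- p = 0.49: c = 0.025, m = 0.399/0.49 = 0.814. At r = 0.7 the fall is 0.3 × 0.814 = 0.24 SD.
- p = 0.143: c = 1.067, m = 0.226/0.143 = 1.58. At r = 0.7 the fall is 0.3 × 1.58 = 0.47 SD.

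**Chance of significance.** The variance of the change in the selected group is (1 − r)² × (1 + cm − m²) + (1 − r²). For p = 0.49 and r = 0.7 this is 0.09 × 0.358 + 0.51 = 0.542, SD 0.736, so t ≈ 0.244/(0.736/√147) = 4.0. For p = 0.143 it is 0.09 × 0.191 + 0.51 = 0.527, SD 0.726, so t ≈ 0.474/(0.726/√43) = 4.3. A normal approximation to the paired test, two-sided, gives:

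| Share selected | r | Fall (SD) | P(p < 0.05) | P(p < 0.05/3) |
|---|---|---|---|---|
| 49% (147) | 0.6 | 0.33 | 99.7% | 99.0% |
| | 0.7 | 0.24 | 98% | 95% |
| | 0.8 | 0.16 | 90% | 80% |
| | 0.9 | 0.08 | 61% | 44% |
| 14.3% (43) | 0.6 | 0.63 | 99.9% | 99.6% |
| | 0.7 | 0.47 | 99% | 97% |
| | 0.8 | 0.32 | 93% | 85% |
| | 0.9 | 0.16 | 66% | 49% |

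**Transitions.** In a simulation with no effect and r = 0.7, 26% of the insecure group (0.26 × 147 ≈ 38) fall below the cut at follow-up in the 49% case, and 49% (0.49 × 43 ≈ 21) in the 14.3% case. The score distribution has not moved, so the same numbers are expected to cross the other way: 38 of 153 and 21 of 257. Counting one direction shows success; counting both shows no net change.

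**Dependence on the clustering inputs.** Null simulation: 300 adolescents, three visits, two-means clustering on T0, one-way repeated-measures ANOVA in the selected cluster (about 150), r from 0.6 to 0.9, correlation 0.3 between true scores, independent visit errors, no class effects, 600 runs per setting. False-positive rates:

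| Clustering on | Food insecurity | A second outcome |
|---|---|---|
| Food-insecurity score alone | 61% to 99.8% | 4% to 5% (not clustered) |
| Three T0 variables | 16% to 65% | 18% to 53% (clustered) |

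**All 300, no selection.** The rate for food insecurity is 3% to 6%, close to the nominal 5%.

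**Secure versus insecure as a between factor.** The expected null difference in change is (1 − r) × φ(c)/[p(1 − p)]. At r = 0.7 this is 0.3 × 0.399/0.250 = 0.48 SD for 49%, and 0.3 × 0.226/0.1226 = 0.55 SD for 14.3%. In the simulation the T0 to T2 contrast between groups was falsely significant in 85% to 100% of runs when clustering on the food-insecurity score alone.

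**The case against.** The strongest reply is that the protocol does not say the full sample is dropped, and does not say the group is formed on the outcome then tested. Several parts of it stand.

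- A reader might infer that Study 5 analyses only the food-insecure adolescents. The text does not support this. Its preceding sentence covers several indicators without restriction, the endpoints and hypothesis (i) concern the adolescents generally, and the factorial ANOVA may use secure versus insecure as a factor. That factor would not rescue the inference, because the interaction carries the same artefact.
- A reader might infer that every Study 5 outcome will appear to improve. That is not supported either. The examples named in section 8.4 (anthropometry, eating attitudes, body image) need not shift if they were not clustering inputs and do not share T0 error with them. Food insecurity is not among those examples, but the list is open and section 5.4 makes it a primary endpoint.
- Cluster analysis is not the cause. A fixed cut-off on T0 data would regress too; clustering adds a boundary that is not stated. Combining the parents' and adolescents' questionnaires is a plausible reason to cluster.
- A reader might infer from the November 2016 date for Study 1, after follow-up ends in March 2016, that the grouping will be made with outcomes known. November 2016 is a manuscript submission date. The protocol gives no classification date.
- The magnitudes depend on an assumed r and on borrowed prevalences. At r = 0.9 the fall is only 0.08 to 0.16 SD.

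If section 7.2 were right about a control group, a randomised comparison would offset the artefact. No such group is described, so this remains a contradiction to resolve and not an answer.

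**Conclusion.** The concern holds for food insecurity in the T0-selected group, and for any other outcome used in the clustering or sharing its T0 error. With no effect, an apparent improvement is expected there, though not certain in any one sample. If selection is on the food-insecurity score alone, the probability of an unadjusted significant result is 61% to 99.9% over the stated range of r, and 44% to 99.6% after Bonferroni for three comparisons. Clustering on several variables weakens the bias without removing it. The conclusion rests on two things in the protocol: selection and reference both use T0, and no control arm is described. The size rests on assumptions the protocol does not supply. The point does not extend to the full-sample analyses, nor to outcomes unconnected with the classification.

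**What to change.** In sections 8.4 and 11.2:

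1. Make all enrolled adolescents the analysis set for the Study 5 impact conclusion, on food insecurity and the other endpoints.
2. Report food-insecurity transitions in both directions, insecure to secure and secure to insecure.
3. Present results in the T0-defined food-insecure group, including any baseline-status-by-time interaction, as descriptive only, with a stated regression-to-the-mean caveat and no claim of impact.
4. Fix the classification rule on T0 data, with its input variables and boundary, before T1 data are analysed.

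Reconcile the randomised, controlled wording in section 7.2 with the single-group design described elsewhere.

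The cost is wording and a smaller apparent effect; no new data are needed. The change removes the selection bias only. Without a comparator, secular and seasonal change and the effect of repeated testing still cannot be separated from the intervention, and the report should say so.

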### 9. Potential risks and benefits

Risks for the participation in this study are not expected, either for parents as for children.

Additionally, the participation in this study might have some benefits for its participants. This study will provide relevant information on healthy eating and physical activity. Thus, it might contribute for a healthy life-style of the participants.

### 10. Project schedule

This project will start in June 2015, although some of the materials have already started to be developed. Baseline evaluation is planned for September 2015. The planned data for completion the follow-up evaluation is March 2016.

### 11. Statistical and analytical plan

### 11.1. Sample size

We expect to include 300 adolescents in the study (6 classes from each school).

### 11.2. Statistical methods

Quantitative analysis will be performed with SPSS and AMOS. In the quantitative analysis, continuous variables will be reported as mean and standard deviation. Qualitative analysis will be performed with NVivo program.

In Study 1, we will perform clusters analysis in order to identify adolescents with food insecurity. In Study 2, we will perform structural equations modeling in order to analyze whether well-being is a mediator variable between food insecurity and disordered eating, and whether sex is a moderator variable. Multilevel analysis will be performed in Study 3. In Study 4, in order to analyze the qualitative data we will conduct Thematic Analysis (NVIVO program). Finally, in Study 5, we will conduct repeated-measures factorial ANOVASs for each variable; the analyses will be complemented with multiple comparisons using Bonferroni adjustment at p < .05.

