### 5.2. Primary objectives

- To improve nutritional status and eating habits in this adolescent population.
- To study the evolution of the variable "Food insecurity" (T0-T1-T2) in this population.

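### Cluster analysis decides which adolescents are food insecure in Study 1, so the label, and with it Study 5's target group, is tied to no fixed level on the endpoint questionnaire

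*Protocol*

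**What the plan says.** Section 11.2 gives the method: "In Study 1, we will perform clusters analysis in order to identify adolescents with food insecurity". It does not state the input variables, the number of clusters or the rule for calling a cluster food insecure. Section 8.4 gives Study 1, on T0 data, two aims: "We will identify: adolescents with food insecurity; and variables associated with food insecurity".

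Elsewhere the construct is measured by questionnaire. Section 5.4 has as a primary endpoint "Changes in food insecurity in households (based on the Food Insecurity Questionnaire) at 3 and 6 months". Section 8.3 says that "parents will answer to the food security questionnaire", to capture the economic determinant, and gives adolescents a separate physical and eating health form "to evaluate the contextual determinants of food security". The same questionnaires are applied at T0, T1 and T2 (section 6). The protocol states no score, cut-off or category for the parent questionnaire.

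The Study 1 label is used again. For Study 5, section 8.4 says: "we aim to study the impact of the intervention on the adolescents who were identified as food insecure in study 1".

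**The concern.** The protocol has two routes to the statement that a pupil is food insecure: a questionnaire, which carries the endpoint, and a cluster label, which carries Studies 1 and 5. Nothing requires them to agree.

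A questionnaire cut-off marks a fixed level of insecurity. A cluster boundary marks the worse-off part of whichever pupils were enrolled, and it moves with the number of clusters. The method returns a top group whether few or most families are insecure.

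Two things are at stake. One is Study 1's main result, namely who and how many are food insecure. The other is the size and membership of the group on which Study 5 judges the intervention. A further risk, conditional on the inputs, is that Study 1 tests for association the same variables that formed its groups.

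**Working it through.** The protocol gives no expected number labelled, no cut-off and no power calculation, so there is no figure to reproduce. The only input taken from it is the sample size: "We expect to include 300 adolescents in the study (6 classes from each school"). Everything else below is assumed, and the results illustrate behaviour, not trial figures. Clustering is k-means, which chooses k centres to minimise the sum of squared distances from each pupil to the nearest centre. The food-insecure group is taken to be the cluster with the highest centre on the insecurity measure.

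**1. No subgroups at all.** One normally distributed score, 300 pupils, 100 samples. On one score, the boundary between neighbouring clusters is the midpoint of their centres. Adding the same amount to every score shifts the boundary by that amount and labels the same pupils. The absolute level of insecurity therefore plays no part.

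| Clusters | Share in top cluster | Of 300 |
|---|---|---|
| 2 | 50.2% | 0.502 × 300 ≈ 151 |
| 3 | 27.1% | 0.271 × 300 ≈ 81 |
| 4 | 16.9% | 0.169 × 300 ≈ 51 |

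**2. Cluster label against a fixed cut-off.** Assumed scale: eight yes/no items, item difficulties evenly spaced from −1.5 to 1.5, logistic slope 1.7, latent severity normal with SD 1.5, assumed cut-off of three or more items. Clusters are formed on the eight items; 100 samples of 300 per row.

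| Mean severity | At or above cut-off | Top of 2 | Top of 3 | Top of 4 |
|---|---|---|---|---|
| −3 | 7.6% | 20.1% | 9.2% | 5.7% |
| −2 | 21.6% | 30.0% | 16.8% | 11.5% |
| −1 | 43.1% | 41.4% | 24.6% | 18.4% |
| 0 | 67.6% | 50.5% | 32.2% | 25.3% |
| 1 | 86.4% | 58.9% | 42.6% | 37.3% |

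The cut-off share rises by 86.4 − 7.6 = 78.8 points from the first row to the last. The top of two clusters rises by 58.9 − 20.1 = 38.8 points. In the middle row, the cut-off labels 0.431 × 300 ≈ 129 pupils; clustering labels about 124, 74 or 55 of the same 300 according to the number of clusters. The sign of the disagreement is not constant: two clusters over-label in the first two rows, nearly agree in the third and under-label in the last two.

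**3. Is the search for associated variables circular?** One score and five variables generated independently of it, two clusters, a t-test at 0.05 on each of the five, 300 samples. If the five tests were independent, the chance of any rejection would be 1 − 0.95^5 = 22.6%.

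| Cluster inputs | Rejections per unrelated variable | Any of five |
|---|---|---|
| Score only | 4.9% | 22.0% |
| Score plus the five variables | 79.7% | 100% |

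With the score alone, the tests behave as they should. With the candidate variables among the inputs, they do not. The protocol does not say which case applies.

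**The case against.** - **Details may sit in a statistical analysis plan.** The algorithm, inputs and number of clusters may well be there. This stands for the details. It does not stand for the choice of clustering as the classifier, which section 11.2 fixes.
- **The protocol describes no questionnaire scoring that is being set aside.** This stands. A reader might infer that published scoring is discarded, but no score or cut-off appears in the document, and clustering could be run on the questionnaire's own items. Even then the boundary would be relative to the sample.
- **Study 1 concerns adolescents, and the endpoint concerns households.** Parents report the economic side and adolescents the contextual side, so combining the two is a reason to cluster. This stands as a cost of the fix. It does not justify a second, unanchored definition, because the protocol itself bases the food-insecurity endpoint on the questionnaire.
- **The primary objective is safe.** A reader might infer that a cluster label cannot serve the aim "To study the evolution of the variable" of food insecurity over T0 to T2. The document does not support that: Study 1 uses T0 data only, nothing says clusters are re-formed later, and the change endpoint uses the questionnaire.
- **No external comparison is planned.** The 14.3% and 49.0% in section 4 are background figures, so lack of comparability with them breaks no stated aim.

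**Conclusion.** The point holds in a limited form. Section 11.2 makes a sample-relative rule the definition of a food-insecure adolescent, although the protocol already collects the measure on which its endpoint rests. The number labelled can change about threefold with the number of clusters alone (151 against 51 of 300 in the homogeneous example), and Study 5's target group inherits that choice.

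The size is illustrative. It rests on k-means, on two to four clusters and on assumed scales, and neither the amount nor the direction of mislabelling in this trial can be derived from the document. I also take the questionnaire in section 5.4 and the parent questionnaire in section 8.3 to be the same instrument.

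A reader might go further and call Study 1's list of associated variables circular. That follows only if candidate correlates, such as the adolescent contextual items, are cluster inputs, and the inputs are not stated. The T0 to T2 change endpoint is not directly affected. The change is worth making because it is nearly free and because Study 5 depends on the label.

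**What to change.** In sections 11.2 and 8.4:

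- Define food insecurity by a Food Insecurity Questionnaire score and cut-off specified before the T0 data are analysed, using the instrument's validated scoring where it exists, and consistent with the primary endpoint.
- Use that definition to label pupils in Studies 1 and 5.
- Analyse associated variables in Study 1 by regression of that score or category on the candidate variables.
- Keep cluster analysis, if wanted, as descriptive profiling, with no association tests on variables used to form the clusters.

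The cost is wording only, since the questionnaire is already planned at all three evaluations. There are two downsides. The exploratory typology no longer defines food insecurity. The label also reflects the parents' household-level report, so the adolescent contextual items are analysed as correlates and do not contribute to the label.
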